4.6.2 Adverse Events

For each recorded adverse event (AE), the term entered by the investigator describing the event (the "reported term") will be assigned a standardized term (the "Preferred Term" [PT]) and assigned to a superclass term (the "System Organ Class" [SOC]) based on the latest version of Medical Dictionary for Regulatory Activities (MedDRA).

Treatment emergent adverse events (TEAEs) will be summarized by SOC and PT. At each level of summarization (at least one event, SOC and PT), patients reporting more than one AE will be counted only once. For TEAEs by grade (intensity), the highest grade will be reported. The table results will be sorted by descending frequency of SOC and PT within each SOC.

Definitions

Treatment emergent adverse events (TEAE): AEs with an observed or imputed date of onset on or after the start date of trial treatment. If the onset date of the AE is prior to the day of first dose, the AE will be considered treatment emergent only if the most extreme intensity is greater than the initial intensity (i.e., the intensity for a given AE increases and its end date is on or after the date of the first dose). An AE with a completely missing, non-imputed start date will be assumed to be treatment emergent unless the AE has a complete, non-imputed end date that is prior to the date of the first dose.

Imputation of incomplete date: in order to evaluate if an AE is treatment-emergent, incomplete dates will be imputed as follows:

- 1. If year is not missing and is after the year of first dose:
 - a. If month is missing, then month will be imputed as January.
 - b. If day is missing, then day will be imputed as the first of the month.
- 2. If year is not missing and is the same as the year of the first dose:
 - a. If month is missing, then impute the month as the month of the first dose date.
 - b. If day is missing, and the month is the same as the month of the first dose date, then impute day as the day of the first dose date.
 - c. If day is missing but month is after the month of first dose date, then impute day as the first day of the month.
- 3. If year is missing then impute the year as the year of the first dose date:
 - a. If month is missing, then impute the month as the month of the first dose
 - b. If day is missing, then impute the day as the day of the first dose date.

- 4. If the start date is completely missing, but the AE is either ongoing or the end date is after the first dose date then impute the start date as the first dose date.
- 5. For any cases involving the rules above, if the AE end date is before the AE start date, then leave the AE start date missing and assume that AE is treatment emergent for the purpose of the analysis. Further, if the AE end date is complete and occurs prior to first dose date, leave the AE start date missing and assume that AE is not treatment emergent.

Output Conventions

All analyses of AE data will be performed using the PTs unless otherwise specified.

For all summary tables, the AEs will be sorted by SOC (in decreasing order of overall incidence) and then by PT (in decreasing order of overall incidence). All summaries and listings of AEs will be based on the Safety-evaluable population. Summaries of AEs will be generated to summarize the incidence of treatment emergent AEs only (TEAE and AE are used exchangeable).

Frequency tables, including patient incidence rates will be provided for the events listed below. For ocular AEs, events in the study eye and fellow eye will be summarized separately:

Overview of AE, including

- Ocular AEs and Serious ocular AEs (SAEs)
- Non-Ocular AEs and Serious non-ocular AEs (SAEs)
- Ocular AEs and SAEs leading to study drug discontinuation
- Non-Ocular AEs and SAEs leading to study drug discontinuation
- Adverse events of special interest defined as follows:
 - Case of an elevated ALT or AST in combination with either an elevated bilirubin or clinical jaundice, as defined in protocol
 - Suspected transmission of an infectious agent by the study drug
 - Causes a decrease of >= 30 letters in VA Score lasting more than 1 hour
 - Requires surgical or medical intervention to prevent permanent loss of sight
 - Associated with severe intraocular inflammation
- Ocular AEs and Serious AEs (SAEs) related to the study treatment (only for study eye)
- Ocular AEs and Serious AEs (SAEs) related to the Anti-VEGF therapy (only for fellow eye)
- Non-Ocular ATE (Arterial Thromboembolic Events) and Cerebrovascular

Hemorrhagic

- AEs of Intraocular Inflammation
- AEs of retinal vascular occlusive disease
- Deaths
- AE of Infectious endophthalmitis
- AE of Rhegmatogeneous retinal detachment
- AE of Retinal tear
- AE leading to study discontinuation

Summary tables presenting the number and percentage of patients who experienced an AE will be summarized by SOC and PT. The AE by severity (mild, moderate, severe) will be also tabulated by SOC and PT.

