5.3.1 Adverse Event Reporting Period

Investigators will seek information on adverse events at each patient contact. All adverse events, whether reported by the patient or noted by study personnel, will be recorded in the patient's medical record and on the Adverse Event eCRF.

After informed consent has been obtained but prior to initiation of study drug, only serious adverse events caused by a protocol-mandated intervention (e.g., invasive procedures such as biopsies, discontinuation of medications) should be reported (see Section 5.4.2 for instructions for reporting serious adverse events).

After initiation of study drug, all adverse events will be reported until the SFV (≥28 to <35 days from last study treatment). For patients who terminate study treatment and from the study early, all adverse events will be reported up to the ETV. For patients who discontinue study treatment early but continue to participate in the study, adverse events will be reported until their last or final study visit.

Instructions for reporting adverse events that occur after the adverse event reporting period are provided in Section 5.6.

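### When an adverse event has a recorded month but no year, the SAP's imputation rule can date a post-New-Year event before first dose and drop it from the treatment-emergent summaries

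*SAP*

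**What the plan says.** SAP 4.6.2 (Adverse Events) counts as treatment emergent "AEs with an observed or imputed date of onset on or after the start date of trial treatment", so an imputed date decides the matter as fully as an observed one. For an onset before first dose there is one exception: "the AE will be considered treatment emergent only if the most extreme intensity is greater than the initial intensity", with an end date on or after first dose.

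Rule 3 of the imputation list covers a missing year: "If year is missing then impute the year as the year of the first dose date". Its two sub-rules act only on parts that are also missing: "If month is missing, then impute the month as the month of the first dose" and "If day is missing, then impute the day as the day of the first dose date". A recorded month is left alone.

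For a start date with nothing recorded, the section leans the other way: "An AE with a completely missing, non-imputed start date will be assumed to be treatment emergent", unless a complete end date precedes first dose. The output conventions in the same section restrict the adverse event summaries to treatment-emergent events.

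Protocol 5.3.1 limits what is reported between consent and first dose to "only serious adverse events caused by a protocol-mandated intervention".

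**The concern.** Follow-up lasts about half a year and the study about 26 months, so many patients are followed across a 1 January. Rule 1 of the same list provides for events in the year after first dose; rule 3 does not. Rule 4 already covers start dates that are wholly missing for events that are ongoing or end after first dose. The main separate job of rule 3 is therefore the event with a month and no year, which is where it fails.

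The result conflicts with the section's own presumption that an event of unknown date is treatment emergent. It also puts events in a period when almost none are collected. At stake are the counts for every summarised category, including events of special interest, intraocular inflammation and endophthalmitis. With 99 patients (SAP 2.3), one lost event can change a rare-event row from 1 to 0.

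**Working it through.** The plan states no figure that depends on this rule, so there is nothing to reproduce. The check is to apply the rules to dates.

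**Inputs.**
- Imputation rules 1 to 5 and the treatment-emergent definition: SAP 4.6.2.
- Last study day: about 168 to 175 days after enrolment (SAP 2). The visit windows in Protocol Appendix 1 give an upper bound of 140 + 7 + 35 = 182 days.
- Assumptions: first doses spread evenly over a 365-day year, onsets spread evenly over follow-up, intensity not worsening.

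**Step 1: one event.** First dose 15 November 2021, true onset 10 February 2022, year not recorded.

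| Start date recorded | Date assigned | Classified as |
|---|---|---|
| Day and month | 10 February 2021 | before treatment |
| Month only | 15 February 2021 | before treatment |
| Nothing | 15 November 2021 | treatment emergent |

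**Step 2: do the other rules catch it?** Rule 4 begins "If the start date is completely missing, but the AE is either ongoing or the end date is after the first dose date"; here the start is only partly missing, so it does not apply. Rule 5 acts when the end date precedes the imputed start. Here the imputed start is too early, so the end date follows it and rule 5 is not triggered. Only the worsening-intensity exception can bring the event back.

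**Step 3: which events are affected?** Follow-up is at most 182 days, so an onset in the next calendar year always falls in an earlier calendar month than first dose. Putting it in the first-dose year therefore always gives a date before first dose. Enumerating every first-dose date against every onset day, for events with month recorded and year missing:
- next-calendar-year onsets dated before first dose: 100%;
- same-calendar-year onsets dated before first dose: 0%.

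With the whole date missing, 0% are dated before first dose. (A day recorded with neither month nor year could also be misdated, but that pattern is unlikely and is not part of this point.)

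**Step 4: how common are next-year onsets?** An onset k days after first dose falls in the next year with probability k/365. Averaged over k = 0 to D, the share is D/(2 × 365):
- D = 168: 168/730 = 0.230
- D = 175: 175/730 = 0.240
- D = 182: 182/730 = 0.249

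This is a share of all post-dose onsets. It would have to be multiplied by the fraction of events with a month but no year, which the documents do not give.

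**The case against.** The strongest reply is that the trigger should hardly ever occur. Events are sought at every contact (Protocol 5.3.1), and treatment visits are 28 days apart (Appendix 1). Discrepant data are queried (7.1), source data are verified (7.3), and the database is cleaned before lock (SAP 2.4). Serious events and events of special interest are to be entered within 24 hours of the site learning of them (Protocol 5.4.2.2), so a missing year is least likely where it would matter most. This stands as an argument about size. It does not make the rule correct for the events it does reach.

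A reader might also infer more than the documents support:
- *That the rule can only remove events.* It can add them. Take a first dose on 10 January 2022 and a procedure-related serious event in December 2021, ongoing and recorded as December with no year. Rule 3 gives December 2022, and a pre-dose event becomes treatment emergent. Given Protocol 5.3.1, this should be rarer than the loss.
- *That every missing-year event after New Year is lost.* Events with no month or day recorded are dated at first dose and kept. Events that worsened and ended on or after first dose are also kept.
- *That 168/365 = 46% measures the error.* Under even enrolment that is the share of patients whose follow-up crosses 1 January, not a share of events.
- *That affected events vanish from the report.* The restriction to treatment-emergent events is stated for the summaries. The listings are based on the safety-evaluable population without that stated limit, so the events may still appear there.

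**Conclusion.** The point holds for one defined pattern: month recorded, year missing, true onset in the calendar year after first dose. Every such event is dated before treatment and leaves the summaries unless the worsening-intensity exception applies. This follows from the SAP text and needs no assumption beyond follow-up of less than half a year.

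The 23% to 25% share of post-dose onsets that fall in the next calendar year rests on evenly spread first doses and onsets. The number of events actually affected cannot be calculated from the documents and is probably very small. The documents do not support a claim that the safety tables are materially biased. The case for changing the rule is that it gives a wrong answer, contradicts the section's own presumption and is easy to correct.

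**What to change.** Replace rule 3 for events with a known month and a missing year:

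1. Use the earliest year that puts the date on or after first dose. If the day is missing, use the first of the month, except in the first-dose month, where the first-dose day is used.
2. If the resulting date is after the event's end date or the patient's exit from the study, leave the start missing and treat the event as treatment emergent, unless a complete end date precedes first dose.

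In the working example the start becomes 10 February 2022 (day recorded) or 1 February 2022 (day missing), both treatment emergent. No post-dose onset with a recorded month is then dated before first dose. The first-of-month convention also avoids impossible dates, such as 30 February when first dose was on the 30th.

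The cost is a short edit to the SAP and to the adverse event derivation program, with no new data. The downside is that a rare pre-dose screening event may be counted. With a first dose on 10 March 2022, an ongoing serious screening event recorded as February with no year is now correctly dated before dose; under the fix, February 2023 lies after study exit, so the event would be presumed treatment emergent. That is the conservative direction and matches how the SAP already treats a wholly missing start date.

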4.4.1 Permitted Therapy

Patients who use concomitant medications should continue their use. Of note, the following are some common therapies that are permitted:

- Onset of ocular hypertension or glaucoma in the study eye during a patient's study participation should be treated as clinically indicated.
- Onset of cataract or posterior capsular opacification in either eye during a patient's study participation may be treated as clinically indicated. Dose interruption criteria (see Section 5.1.2.2, Section 5.1.2.3, and Table 3 may apply if cataract surgery is required.
- Short-term use of topical ocular corticosteroids after cataract surgery, yttrium-aluminum garnet capsulotomy, peripheral iridotomy, argon/selective laser trabeculoplasty, or ocular allergic conditions.

Fellow (Non-Study) Eye Treatment with Anti-VEGF Therapy

At the discretion of the investigator, the patient's fellow eye (non-study eye) may be treated with anti-VEGF therapy licensed for ocular use if they are diagnosed with an ocular condition for which the selected anti-VEGF therapy (except brolucizumab) is approved by the country regulatory agency (SOC). Should the fellow eye require treatment during the study, the Sponsor will cover the cost of the approved licensed ocular anti-VEGF therapy (except brolucizumab and Susvimo ™) in accordance with local regulations, until faricimab is made available in that region, after which the Sponsor will support fellow-eye treatment with faricimab as long as the patient remains in the study. Any exceptions for ongoing reimbursement of other anti-VEGF therapies must be approved by the Sponsor.

Fellow eye treatment reimbursement will cease if the patient is discontinued from faricimal study treatment. Fellow eye treatment reimbursement will cease once the patient has completed the trial.

Study eye treatment and fellow eye treatment with anti-VEGF agents may be done at the same study visit; however, the study eye should receive study treatment per protocol

prior to anti-VEGF treatment in the fellow eye. *Note: Bevacizumab is not licensed for ophthalmic use in any country; therefore, it is prohibited to be used.*

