5.3.4 Assessment of Causality of Adverse Events

Investigators should use their knowledge of the patient, the circumstances surrounding the event, and an evaluation of any potential alternative causes to determine whether an adverse event is considered to be related to the study drug, indicating "yes" or "no" accordingly. The following guidance should be taken into consideration (see Table 5):

- Temporal relationship of event onset to the initiation of study drug
- Course of the event, with special consideration of the effects of dose reduction, discontinuation of study drug, or reintroduction of study drug (as applicable)
- Known association of the event with the study drug or with similar treatments
- Known association of the event with the disease under study
- Presence of risk factors in the patient or use of concomitant medications known to increase the occurrence of the event
- Presence of non-treatment-related factors that are known to be associated with the occurrence of the event

Table 5 Causal Attribution Guidance

Is the adverse event suspected to be caused by the study drug on the basis of facts, evidence, science-based rationales, and clinical judgment?

- YES There is a plausible temporal relationship between the onset of the adverse event and administration of the study drug, and the adverse event cannot be readily explained by the patient's clinical state, intercurrent illness, or concomitant therapies; and/or the adverse event follows a known pattern of response to the study drug; and/or the adverse event abates or resolves upon discontinuation of the study drug or dose reduction and, if applicable, reappears upon re-challenge.
- An adverse event will be considered related, unless it fulfills the criteria specified below. Evidence exists that the adverse event has an etiology other than the study drug (e.g., preexisting medical condition, underlying disease, intercurrent illness, or concomitant medication); and/or the adverse event has no plausible temporal relationship to administration of the study drug (e.g., cancer diagnosed 2 days after the first dose of study drug).

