- o After AH tap (of the study eye; at the applicable visits) and faricimab IVT injection (in the study eye, at the applicable study visits) and, if applicable, the anti-VEGF treatment (in the non-study eye), a clinical safety check (including IOP measurement, slit lamp examination, and dilated binocular indirect high-magnification ophthalmoscopy) needs to be performed prior to releasing the patient.
- P Samples are collected from the study eye only. Performed prior to the faricimab IVT injection in the study eye.
- May only be performed after the AH tap (study eye only) and if patient is a WOCBP, their pregnancy test (urine) must be negative. Only the study eye will receive the faricimab IVT injection.
- The finger-counting test should be conducted within approximately 15 minutes of study treatment administration for the study eye and, if applicable, the non-study eye (fellow eye).

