4.1 ANALYSIS POPULATIONS

4.1.1 Modified Intent-To-Treat Population

The modified intent-to-treat (mITT) population is defined as all patients enrolled in the study that received any amount of study treatment.

4.1.2 Per Protocol Population

Not Applicable.

4.1.3 Pharmacokinetic-Evaluable Population

Not Applicable.

4.1.4 Safety-Evaluable Population

Safety-evaluable population (SE) is defined as all patients enrolled who received at least one injection of study treatment.

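### The incidence of fellow-eye adverse events related to anti-VEGF therapy is taken over all safety-evaluable patients, including those whose fellow eye was never injected, so it understates the rate among treated patients

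*SAP*

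**What the plan says.** SAP 4.6.2 (Output Conventions) states: "All summaries and listings of AEs will be based on the Safety-evaluable population". SAP 4.1.4 defines that population as "all patients enrolled who received at least one injection of study treatment", with no condition on the fellow eye.

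The same part of SAP 4.6.2 says "Frequency tables, including patient incidence rates will be provided for the events listed below", and the list includes "Ocular AEs and Serious AEs (SAEs) related to the Anti-VEGF therapy (only for fellow eye" (closing bracket omitted). The bracketed words restrict the eye, not the patients in the denominator. No subset of patients with a treated fellow eye is defined anywhere in the SAP. SAP 4.6.1 describes fellow-eye anti-VEGF exposure (duration, number of administrations, diagnosis) but does not link it to the adverse-event tables.

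Protocol 4.4.1 makes this treatment discretionary: "the patient's fellow eye (non-study eye) may be treated with anti-VEGF therapy licensed for ocular use", provided the eye has an approved indication. It is separate from study treatment, since Protocol Appendix 1 says "Only the study eye will receive the faricimab IVT injection".

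On causality, Protocol 5.3.4 asks investigators to decide whether "an adverse event is considered to be related to the study drug", answered yes or no. In Table 5, concomitant medication appears only as an alternative cause that supports a no.

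**The concern.** A patient whose fellow eye is never injected cannot have an event caused by fellow-eye anti-VEGF, yet is counted in the denominator. The printed percentage then reflects how many fellow eyes happened to be treated as well as how often treatment caused harm. A reader who takes it as the risk of fellow-eye injection would take too low a figure. With no events, the data would seem to exclude a risk that they cannot exclude.

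The SAP applies the at-risk principle elsewhere: in the time-to-resolution analyses of retinal fluid (SAP 4.4.1.1), patients without fluid at baseline are left out because they are not at risk. Nothing equivalent is said for this row.

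The second gap is the source of the attribution. The row needs a judgement about an agent other than the study drug, and the protocol describes no such judgement. This matters in practice because Protocol 4.4.1 foresees fellow-eye faricimab once it is available in a region. An answer about the study drug might then not show which injection was meant.

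**Working it through.** **Inputs**

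- Denominator as written: safety-evaluable patients, N (SAP 4.6.2 and 4.1.4).
- N = 99 for illustration. SAP 2.3 reports an increase to at most 99 patients, so this is an upper limit.
- x: patients with at least one fellow-eye event related to anti-VEGF. The documents give no count; x = 2 and x = 0 are assumptions.
- f: fraction of safety-evaluable patients whose fellow eye is treated. The documents do not give it; the range below is an assumption.

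The plan states no rate for this output, so there is no figure to reproduce.

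**Formula**

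A related event needs a treated fellow eye, so the numerator x is the same either way.

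- Rate as the SAP would print it: x / N
- Rate among treated patients: x / (fN)
- Printed rate = f × rate among treated; understatement factor = 1/f

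**Numbers**

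On all 99 patients, x = 2 gives 2/99 = 2.0% (exact 95% interval 0.2–7.1%). With x = 0 the upper limit is 1 − 0.025^(1/99) = 3.7%. On treated patients, with n = 99f rounded:

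| f (assumed) | Treated n | Factor 99/n | x = 2: rate among treated (95% interval) | x = 0: upper limit |
|---|---|---|---|---|
| 0.2 | 20 | 4.95 | 10.0% (1.2–31.7%) | 16.8% |
| 0.3 | 30 | 3.30 | 6.7% (0.8–22.1%) | 11.6% |
| 0.5 | 50 | 1.98 | 4.0% (0.5–13.7%) | 7.1% |
| 0.75 | 74 | 1.34 | 2.7% (0.3–9.4%) | 4.9% |
| 1 | 99 | 1.00 | 2.0% (0.2–7.1%) | 3.7% |

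Intervals are two-sided Clopper–Pearson. They are shown to indicate precision; SAP 4.6.2 does not specify intervals for adverse events.

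The factor depends only on f, not on x or N (small departures from 1/f come from rounding n). The direction is fixed for any f below 1. The zero-event column shows that an empty row on 99 patients looks more reassuring than the same row on 30 or 50.

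**The case against.** The strongest reply is that x/N is not wrong in itself. It is the share of study patients who had such an event, which is what a patient incidence on a safety population usually means, and the numerator is complete. SAP 4.6.1 describes fellow-eye exposure, so a reader could rescale. This stands in part: the percentage on all patients is legitimate if labelled as such, which is why printing both is acceptable. But SAP 4.6.1 does not expressly promise the number of treated patients, and nothing ties it to this row.

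Three stronger readings are tempting, and the documents do not support them.

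- *That the row has no causality data behind it.* The gap is shown only for Protocol 5.3.4 and Table 5. Protocol 5.3 and Appendix 2 have a physician assign causality without naming an agent. The eCRF is not among the documents, and the SAP lists relation to anti-VEGF separately from relation to study treatment, which suggests that a separate field may exist.
- *That the understatement is two- to threefold.* That is what assumed treated shares of 30–50% would give. Neither the share nor any event count is in the documents.
- *That the row biases a comparison between eyes, or serves as evidence about faricimab.* SAP 4.6.2 summarises the two eyes separately and plans no comparison, and the row is labelled as anti-VEGF therapy. A new denominator would not separate agents in any case.

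A remedy based simply on the first fellow-eye injection would also be incomplete. Exclusion criterion 37 shows that some fellow eyes may already be under treatment at entry, so the rule must say on-study.

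**Conclusion.** The point holds for one descriptive output. As written, the SAP yields a percentage equal to f times the rate among patients with a treated fellow eye. The understatement is 1/f: about 5 at f = 0.2, 2.0 at f = 0.5, and none at f = 1. The direction is certain if any fellow eye goes untreated, which an optional treatment makes likely but the documents do not quantify. The size rests entirely on the assumed f.

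On causality, the conclusion is limited to this: the protocol describes no assessment of relation to fellow-eye anti-VEGF, and the SAP does not say which collected item it will use. Whether that item exists cannot be settled from these documents.

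No hypothesis test, sample-size statement or exploratory endpoint depends on the row.

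**What to change.** In SAP 4.6.2, for this row only:

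1. Use patients with at least one on-study fellow-eye anti-VEGF injection as the denominator, or print that percentage beside the one on all safety-evaluable patients. Show the treated n in either case.
2. List separately any related event in a patient whose fellow eye was treated only before the study, so that it is neither lost nor set against the wrong denominator.
3. Name the existing eCRF item that records relation to fellow-eye anti-VEGF. Where an event has already been judged related, an extra onset condition adds little.
4. If no such item was collected, retitle the row as fellow-eye ocular adverse events in anti-VEGF-treated fellow eyes, and count events with onset on or after the first on-study fellow-eye injection. The onset rule is needed here because SAP 4.6.2 otherwise dates treatment emergence from the start of trial treatment.

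The cost is table programming using the fellow-eye exposure data that SAP 4.6.1 already summarises. The downside is a higher, less favourable percentage with a wider interval. Under step 4 the row also stops measuring attributed events. None of this needs new data; adding a causality question to the protocol and eCRF would be a change in data collection and is not proposed.
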